was achieved in an EBV+ PTCL patient whose disease never responded to second-line histone deacetylase inhibitor (HDACi) treatment, and one of the CRs was achieved in an EBV+ DLBCL patient whose disease never responded to first-line R-CHOP chemotherapy. Also notable, 2 patients with DLBCL and 1 patient with ENKTL continued on treatment approximately 39+ months. Three patients (PTCL, ENKTL, HL), who at the time of enrollment in this study were not eligible for SCT or CAR-T-cell therapy, achieved adequate disease control and were able to proceed to SCT (n=1 autologous and n=1 allogeneic) or CAR-T-cell therapy (n=1), which are notable outcomes for heavily pretreated patients with poor prognoses. Four patients remained on study treatment at the time of data cutoff.

As of the data cutoff date (04 May 2023), 64 patients overall were evaluable for safety (Phase 1b: 25 patients, Phase 2: 30 patients, nanatinostat tablet PK cohort: 9 patients). The most common (>20% of patients) treatment-emergent AEs (TEAEs) reported overall were platelet count decreased / thrombocytopenia (16 [25%] and 11 [17.2%]), nausea (25 [39.1%]), neutropenia / neutrophil count decreased (14 [21.9%] and 11 [17.2%]), anaemia (24 [37.5%]), fatigue (22 [34.4%]), constipation and diarrhea (19 patients each [29.7%]), increased blood creatinine (17 [26.6%]), and vomiting (15 [23.4%]). Most TEAEs were Grade 1 or 2 in severity. Most TEAEs were Grade 1 or 2 in severity.

Across all cohorts, the most frequently reported Grade 3/4 TEAEs (>10% of patients) were neutropenia / neutrophil count decreased (12 [18.8%] and 9 [14.1%]), platelet count decreased / thrombocytopenia (6 [9.4%] and 8 [12.5%]), and anaemia (13 [20.3%]). Specifically, among the events of increased creatinine, all were Grade 1 or 2 in severity.

No study drug-related deaths occurred. Serious adverse reactions (n=12) included febrile neutropenia and atrial fibrillation (each n=2, [3.1%]), and anemia, neutropenia, thrombocytopenia, pharyngitis, sepsis, myelodysplastic syndrome, tumor necrosis, and dyspnoea (each n=1 [1.6%]). Thirteen (20%) patients had adverse events resulting in drug withdrawal.

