4.6.2 Adverse Events

Treatment-emergent adverse events (TEAEs) are defined as those AEs with onset after the first dose of study drug or existing events that worsened after the first dose during the study. Treatment-emergent AEs will be summarized by cohort and over all patients combined.

Specific to Cohort 3a, for patients who cross over to receive combination therapy, events that occur during the monotherapy period will be counted in the Cohort 3a monotherapy subcohort only. Events that occur after the end of monotherapy but prior to the first date of treatment within the combination period will also be counted in the Cohort 3a monotherapy subcohort only. Events occurring after the start of combination therapy will be counted in the Cohort 3a crossover subcohort only.

Events reported with a partial onset date (e.g., month and year are reported but the day is missing) will be considered to be treatment-emergent if it cannot be confirmed that the event onset was prior to the first dose of study drug based on the available date entries.

Verbatim terms on case report forms will be mapped to preferred terms and system organ classes using MedDRA, version 26.0.

Summaries that are displayed by system organ class and preferred terms will be ordered by descending incidence of system organ class and preferred term within each system organ class. Summaries displayed by preferred term only will be ordered by descending incidence of preferred term. Summaries of the following types will be presented:

- Overall summary of number of unique TEAEs and patient incidence of TEAEs meeting various criteria;
- Overall summary of number of unique treatment-emergent serious adverse events (SAEs) and patient incidence of treatment-emergent SAEs meeting various criteria;
- Patient incidence of TEAEs by MedDRA system organ class and preferred term;
- Patient incidence of the most frequently occurring TEAEs (i.e., TEAEs occurring in ≥ 10% of the Safety Analysis Set) by MedDRA preferred term;

- Patient incidence of TEAEs by CTCAE grade, MedDRA system organ class and preferred term;
- Patient incidence of TEAEs by relationship to nanatinostat, MedDRA system organ class and preferred term;
- Patient incidence of TEAEs by relationship to valganciclovir, MedDRA system organ class and preferred term;
- Patient incidence of TEAEs related to nanatinostat by CTCAE grade, MedDRA system organ class and preferred term;

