- Patient incidence of TEAEs related to valganciclovir by CTCAE grade, MedDRA system organ class and preferred term;
- Patient incidence of TEAEs related to nanatinostat or valganciclovir by CTCAE grade, MedDRA system organ class and preferred term;
- Patient incidence of the most frequently occurring TEAEs related to nanatinostat (i.e., related TEAEs occurring in ≥ 10% of the Safety Analysis Set) by MedDRA preferred term;
- Patient incidence of the most frequently occurring TEAEs related to valganciclovir (i.e., related TEAEs occurring in ≥ 10% of the Safety Analysis Set) by MedDRA preferred term;
- Patient incidence of the most frequently occurring TEAEs related to nanatinostat or valganciclovir (i.e., related TEAEs occurring in ≥ 10% of the Safety Analysis Set) by MedDRA preferred term;
- Patient incidence of TEAEs leading to dose interruption of nanatinostat by MedDRA system organ class and preferred term;
- Patient incidence of TEAEs leading to dose interruption of valganciclovir by MedDRA system organ class and preferred term;
- Patient incidence of TEAEs leading to dose interruption of nanatinostat or valganciclovir by MedDRA system organ class and preferred term;
- Patient incidence of TEAEs leading to dose reduction of nanatinostat by MedDRA system organ class and preferred term;
- Patient incidence of TEAEs leading to dose reduction of valganciclovir by MedDRA system organ class and preferred term;
- Patient incidence of TEAEs leading to dose reduction of nanatinostat or valganciclovir by MedDRA system organ class and preferred term;
- Patient incidence of TEAEs related to nanatinostat leading to discontinuation of study drug by MedDRA system organ class and preferred term;

- Patient incidence of TEAEs related to valganciclovir leading to discontinuation of study drug by MedDRA system organ class and preferred term;
- Patient incidence of TEAEs related to nanatinostat or valganciclovir leading to discontinuation of study drug by MedDRA system organ class and preferred term;
- Patient incidence of SAEs by MedDRA system organ class and preferred term;
- Patient incidence of SAEs by CTCAE grade, MedDRA system organ class and preferred term;
- Patient incidence of SARs (nanatinostat) by MedDRA system organ class and preferred term;
- Patient incidence of SARs (valganciclovir) by MedDRA system organ class and preferred term;
- Patient incidence of SARs (nanatinostat or valganciclovir) by MedDRA system organ class and preferred term;

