- Patient incidence of TEAEs leading to death by MedDRA system organ class and preferred term.

Select AE summaries will also be repeated for different age subgroups (<65 years old, ≥65 years old). Separate AE summaries may also be repeated for adolescents 12-17 years old if there are at least 5 patients enrolled for this age group. Selected AE summaries may be repeated in terms of exposure-adjusted rates in 100 patient-years.

At each level of summarization (e.g., any AE, system organ class, and preferred term), patients experiencing more than one TEAE will be counted only once. In the summary of TEAEs by CTCAE grade, patients will be counted once at the highest severity reported at each level of summarization; in the summary of TEAEs by relationship, patients will be counted once at the closest relationship to study drug. Related events include those reported as "Possibly Related" or "Definitely Related" to study drug; events considered not related are those reported as "Unrelated" to study drug.

For summaries of treatment-related TEAEs by CTCAE grade, a column summarizing patients with at least one treatment-related Grade \geq 3 TEAE will also be presented.

Adverse event data will be presented in data listings by patient, cohort, and event. Serious AEs and AEs leading to permanent discontinuation of the study drugs will also be presented in separate data listings.

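### SAP 4.6.2 defines no grouped term for low platelets or low neutrophils, so if coding splits as in the earlier study, no planned AE table counts the patients affected

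*SAP*

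**What the plan says.** SAP 4.6.2 codes reported events with MedDRA 26.0 to a preferred term and a system organ class, and to nothing between or across these. The main table is "Patient incidence of TEAEs by MedDRA system organ class and preferred term". The tables by grade, relationship, seriousness and dose action follow the same layout, for example "Patient incidence of TEAEs leading to dose interruption of nanatinostat or valganciclovir by MedDRA system organ class and preferred term". The tables of most frequent events use the preferred term alone, with a cut-off of 10% of the Safety Analysis Set. Discontinuation is tabulated for drug-related events.

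The exceptions are two overall summaries, one for TEAEs ("Overall summary of number of unique TEAEs and patient incidence of TEAEs meeting various criteria") and a parallel one for serious events. Their criteria are not defined.

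The counting rule is "At each level of summarization (e.g., any AE, system organ class, and preferred term), patients experiencing more than one TEAE will be counted only once". It names three levels as examples: any event, class and term. Neither SAP 4.6.2 nor Protocol 9.7 names a grouped term, a standardised query or an event of special interest.

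Protocol 1.2.4 reports the earlier study of this combination. For all grades it gives "platelet count decreased / thrombocytopenia (16 [25%] and 11 [17.2"%]) and "neutropenia / neutrophil count decreased (14 [21.9%] and 11 [17.2"%]). For Grade 3/4 it gives "neutropenia / neutrophil count decreased (12 [18.8%] and 9 [14.1"%]) and "platelet count decreased / thrombocytopenia (6 [9.4%] and 8 [12.5"%]). It gives no combined patient count for either pair.

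**The concern.** The same clinical event can be coded as a condition (thrombocytopenia, neutropenia) or as a laboratory finding (platelet count decreased, neutrophil count decreased). Protocol 8.1.1 leaves room for both: a diagnosis is recorded as such, and otherwise the laboratory abnormality is recorded as the event. About 80 sites are expected (SAP 4.5.6.4), and the plan has no convention that brings the two forms together.

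If the terms split, the number of patients with the toxicity lies somewhere between the larger row and the sum of the rows. The tables do not show where. A class row does not help, because it counts any event in that class.

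The incidence and severity of TEAEs is a secondary endpoint, and these are the regimen's main haematological toxicities. The dose-limiting toxicities in the first four patients at the earlier study's first dose level were Grade 4 neutropenia and Grade 3 and Grade 4 thrombocytopenia. Protocol 1.3.2 names thrombocytopenia as a toxicity that the two drugs share. Protocol Table 3 makes both cytopenias grounds for interrupting treatment. A reader would want to know how many patients had either one with a given consequence. No endpoint definition, stage decision or dosing rule depends on the answer.

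**Working it through.** **Inputs.** All counts come from Protocol 1.2.4, with 64 patients evaluable for safety. They are read as patients, because the printed percentages are percentages of 64.

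**Reproducing the stated figures.** 16/64 = 25.0%; 11/64 = 17.2% (printed for both pairs); 14/64 = 21.9%; 12/64 = 18.8%; 9/64 = 14.1%; 6/64 = 9.4%; 8/64 = 12.5%. All eight printed percentages agree.

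**Bounds.** Suppose *a* patients have one term and *b* the other. The number with at least one satisfies max(*a*, *b*) ≤ patients ≤ min(64, *a* + *b*). The lower end is reached if every patient with the rarer term also has the commoner one, and the upper end if no patient has both. The largest single row shows max(*a*, *b*), so it can fall short by 0 up to min(*a*, *b*)/64.

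| Earlier study, N = 64 | Counts by term | Largest single row | Highest possible count | Largest possible gap (points) |
|---|---|---|---|---|
| Low platelets, any grade | 16, 11 | 16 (25.0%) | 27 (42.2%) | 11/64 = 17.2 |
| Low neutrophils, any grade | 14, 11 | 14 (21.9%) | 25 (39.1%) | 11/64 = 17.2 |
| Low platelets, Grade 3/4 | 6, 8 | 8 (12.5%) | 14 (21.9%) | 6/64 = 9.4 |
| Low neutrophils, Grade 3/4 | 12, 9 | 12 (18.8%) | 21 (32.8%) | 9/64 = 14.1 |

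The smallest possible gap is 0 in every row.

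**Febrile neutropenia.** Among the earlier study's serious adverse reactions, febrile neutropenia was reported in 2 patients and neutropenia in 1. A neutropenia group without febrile neutropenia would show 1/64 = 1.6%. With it, the group would show 2 to 3 patients (3.1% to 4.7%). Its membership of the group should therefore be settled before the data are seen.

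**The 10% rule (hypothetical).** Take a safety set of 141, the maximum size of one expanded cohort. A term with 14 patients (14/141 = 9.9%) is dropped from the most-frequent tables. Two such terms could cover up to 28 patients (28/141 = 19.9%) and both be dropped.

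**What other planned outputs supply.** SAP 4.6.4 plans three-by-three low/normal/high shift tables for each laboratory parameter where reference ranges apply. It also plans five-by-five CTCAE grade shift tables for selected parameters and patient listings of Grade 3 or higher abnormalities. Protocol 9.7 adds a summary of clinically significant Grade 3/4 laboratory abnormalities. These show how often counts fell and how far. None carries relationship, seriousness or dose action. Listings under SAP 4.6.2 and 4.6.3 hold those details by patient, and the any-event rows give the overall number of patients with an interruption or reduction.

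**The case against.** The strongest reply is that nothing here is an error. Protocol 9.7 asks for tables by class and preferred term, and the SAP provides them. The laboratory shift tables are arguably the better measure of how often cytopenia occurs: under Protocol 8.1.1 an abnormal value becomes an AE only if it leads to discontinuation, needs treatment or a dose change, or is judged clinically important. The Table 3 triggers for neutropenia and thrombocytopenia are themselves set by blood counts. The figures come from another study whose coding conventions are not given. The dose-limiting toxicities arose at a level that began with valganciclovir 900 mg twice daily, while the regimen used here had none among its 5 patients in dose escalation. All four any-grade terms in the earlier study were at 17.2% or more, so all would have passed a 10% cut-off. The table shells are not among the documents, and the two overall summaries could contain a cytopenia row, though nothing says that they do.

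Most of this stands, and it limits the point. It does not remove it: laboratory tables cannot show how many patients had a related, serious or dose-changing cytopenia, and counting from listings leaves the reader to do what a table should do.

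A reader might infer that the trial will have no count of patients with low platelets or neutrophils. The planned laboratory tables contradict that. A reader might also widen the any-grade neutrophil range by adding the 2 serious febrile neutropenia cases. That would mix serious reactions with all-grade events, and the all-grade febrile neutropenia count is not given.

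**Conclusion.** The point holds as a conditional gap in the AE tables. If coding splits as it did in the earlier study, no planned AE table gives the number of patients with a low-platelet or low-neutrophil event, overall or by grade, relationship, seriousness, interruption, reduction or discontinuation. If coding does not split, the single preferred-term row gives the number and the gap disappears.

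The tabulated ranges are bounds and not estimates, and they carry over to this trial only if coding splits to a similar degree. It is tempting to say that the plan will understate these toxicities. The documents do not support that, because the overlap between terms is not reported. The supported statement is that, with split coding, the AE tables would leave the number undetermined. This is a worthwhile, inexpensive improvement in reporting a secondary endpoint, and it has no bearing on the efficacy conclusions.

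**What to change.** In SAP 4.6.2, define two grouped terms before any analysis:

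- thrombocytopenia: thrombocytopenia and platelet count decreased;
- neutropenia: neutropenia and neutrophil count decreased.

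Count each patient once per group, at worst grade. Show the group rows beside the preferred-term rows in the all-grade, by-grade, relationship, serious, interruption, reduction and discontinuation tables. Apply the 10% cut-off to the groups as well as to the terms.

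Keep febrile neutropenia as its own row, since Protocol Table 3 handles it as a separate toxicity with its own definition. State in advance whether it also counts in the neutropenia group.

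The cost is a short addition to the SAP text, a small look-up in the AE programs and two extra rows per table. The reported incidence of these two toxicities may come out higher than any single preferred-term row would show.

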#### 7.3.2. Safety and Tolerability Assessments

Adverse events will be assessed, and concomitant medications, procedures, and hospitalizations will be recorded from the signing of the ICF until 28 days post-last dose of study treatment.

All 12-lead ECGs will be conducted in triplicate. Average corrected QT interval using Fridericia's method (QTcF) is to be calculated to confirm eligibility. For patients enrolled in any Stage 1 cohort, ECGs will be performed in triplicate, as described in Section 7.3.2.8. ECG tracings will be provided to a central laboratory, instructions are provided in the ECG Manual.

Viral levels [EBV, CMV, HHV-6, HHV-8, and HIV (for HIV+ patients only)] will be monitored for viral reactivation.

Tolerability will be assessed by the incidence of AEs leading to dose modifications or study drug discontinuation.

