## 9.7. Safety Analysis

Safety analysis will be based on all patients in the Safety population and will be summarized overall, by cohort, and by any other relevant subgroup, such as randomization to monotherapy.

Study medication exposure will be summarized for each patient and tabulated by cohort including duration of study medication, total dose taken, and dose reductions.

Adverse events, vital sign measurements, clinical laboratory measurements, and concomitant medications will be summarized overall and by cohort. Tabulations and listings of values for vital signs and laboratory safety evaluations will be presented.

Adverse events will be coded according to MedDRA and classified using the NCI CTCAE Version 5.0. The incidence rates of AEs will be tabulated by System Organ Class and Preferred Term. Subsets of AEs to be summarized include serious AEs (SAEs), events of all CTCAE grade severities, suspected treatment-related AEs, and events that resulted in withdrawal of study medication. The most severe grade of each preferred term for a patient will be utilized for summaries of AEs by NCI CTCAE grade. All AEs with corresponding attributes will be displayed in a by-patient listing. Adverse events leading to death or to discontinuation from treatment, events classified as NCI CTCAE Grade 3 or higher, suspected treatment-related events, all deaths, and SAEs will also be displayed in by-patient listings separately.

Clinical laboratory results will be summarized descriptively by cohort, which will also include a display of change from baseline. Laboratory values outside of the normal ranges will be identified. Clinically significant hematologic and non-hematologic laboratory abnormalities that meet Grade 3 or Grade 4 criteria according to the CTCAE will be listed and summarized. Graphical display of selected lab parameters over the course of study will be provided.

Vital sign measurements will be listed for each patient at each visit. Descriptive statistics for vital signs, both observed values and changes from baseline, will be summarized by cohort.

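### The SAP limits every named table of TEAEs leading to discontinuation to drug-related events, although the protocol's tolerability measure has no relatedness filter; the change is not declared

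*SAP*

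**What the plan says.** Protocol 7.3.2 sets the measure: "Tolerability will be assessed by the incidence of AEs leading to dose modifications or study drug discontinuation". It does not mention relationship to study drug. Protocol 9.7 lists the adverse event subsets that will be summarized. Among them are "suspected treatment-related AEs, and events that resulted in withdrawal of study medication", given as two separate items.

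SAP 4.6.2 names three tables on discontinuation. One counts only events attributed to nanatinostat, and another only those attributed to valganciclovir. The third takes both drugs together: "Patient incidence of TEAEs related to nanatinostat or valganciclovir leading to discontinuation of study drug". All three are broken down by organ class and term.

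In the same list, the tables for dose interruption and dose reduction (by nanatinostat, by valganciclovir, and by either) carry no relatedness restriction. Serious adverse events have all-cause tables as well as separate tables of serious adverse reactions. The table of TEAEs leading to death is all-cause.

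Outside that list, SAP 4.6.2 promises that "AEs leading to permanent discontinuation of the study drugs will also be presented in separate data listings". It also plans an overall summary of TEAE incidence by criteria that it does not specify. SAP 4.8 sets out changes from the protocol: the analysis sets for efficacy and three added secondary efficacy endpoints. It does not mention the discontinuation tables.

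**The concern.** The protocol's tolerability measure has two parts, dose modification and discontinuation. The SAP tabulates the first for all causes and the second only for related events, so the two parts are not on the same footing and cannot be read together.

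The restriction matters in this design. The trial is open-label, and relatedness is the investigator's judgement (Protocol 8.4). Under SAP 4.6.2, an event recorded as unrelated counts as not related and so drops out of all three tables. Underlying disease is one of the alternative explanations that Protocol 8.4 gives for calling an event unrelated, and in relapsed or refractory lymphoma that explanation is often available. Describing the safety of the combination is a secondary objective, and discontinuation because of an adverse event is one of the figures by which readers judge tolerability.

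**Working it through.** The plan states no figure here to reproduce. The check is a comparison of texts, followed by an illustration of how far the two counts could differ.

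**Step 1: what the protocol requires.** Section 7.3.2 asks for an incidence, with no relatedness filter. Section 9.7 places "events that resulted in withdrawal of study medication" beside suspected treatment-related events as a separate subset, so the withdrawal subset is not a part of the related one. Section 9.7 promises by-patient listings in addition, so a listing does not replace the summary.

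**Step 2: what the SAP commits to, by category (4.6.2).**

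| Category | Named all-cause table | Named related-only table |
|---|---|---|
| Dose interruption | yes (3) | no |
| Dose reduction | yes (3) | no |
| Serious events | yes | yes |
| Leading to death | yes | no |
| Discontinuation | **no** | yes (3) |

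Discontinuation is the only one of these categories without a named all-cause table.

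**Step 3: whether another output fills the gap.**

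- *Overall TEAE summary (SAP 4.6.2).* Its criteria are not defined. All-cause discontinuation may be one of them, but nothing commits to it.
- *Listings (SAP 4.6.2 and 4.6.3).* They carry no relatedness filter, but they are patient-level and give no incidence by cohort.
- *Disposition (SAP 4.3.1).* It counts early discontinuation of the study by primary reason. A patient can stop treatment and stay in follow-up (Protocol 7.2.3 and 7.2.6), so this is not discontinuation of study drug because of an adverse event.

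**Step 4: whether the change is declared.** SAP Section 1 says that the SAP supersedes the protocol's analysis plan. Section 4.8 does not list this change.

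**Step 5: illustration of size.** Let A be the proportion of patients with any adverse event leading to discontinuation, and f the share of those patients with at least one such event judged related. The related-only incidence is R = f × A. Since f lies between 0 and 1, R cannot exceed A, and R = A when f = 1.

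Protocol 1.2.4 reports that 13 of 64 safety-evaluable patients in the prior study had adverse events resulting in drug withdrawal: A = 13/64 = 20.3%, in agreement with the 20% stated there. No split by relatedness is given, so f is an assumption:

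| f (assumed) | R = f × 20.3% |
|---|---|
| 100% | 20.3% |
| 75% | 15.2% |
| 50% | 10.2% |
| 25% | 5.1% |

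**The case against.** A reader might infer that the all-cause figure will never be tabulated and that the SAP understates the incidence of discontinuation. The documents support neither statement.

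- The overall TEAE summary has open criteria and might carry an all-cause discontinuation row.
- The three tables are labelled as related, and the SAP nowhere presents them as the tolerability measure or as a headline rate.
- The all-cause listings would let someone rebuild the count.
- The relatedness rules work partly against a large gap. Protocol 8.4 reserves the unrelated category for events whose timing makes a causal link very unlikely and which also have a reasonable alternative explanation. Events that fall clearly into neither outer category are possibly related, and SAP 4.6.2 counts these as related. Many ambiguous events on treatment would therefore stay in the tables.
- Protocol 7.3.2 asks for an incidence, not for a breakdown by system organ class and preferred term. One row in the overall summary could meet that section.
- No efficacy conclusion, decision rule or sample size depends on this point, and TEAE incidence overall is tabulated without a relatedness filter.
- Protocol 1.2.4 does not say outright that the 13 withdrawals were counted regardless of relationship, though that is the natural reading.

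These points limit the claim but do not remove it. A row that might appear is not a commitment, and the SAP says that it exists to avoid post hoc decisions. A listing from which a reader must count is not an incidence. The conflict between the protocol's measure and the named tables remains.

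**Conclusion.** The point holds in this form: SAP 4.6.2 restricts every named table of TEAEs leading to discontinuation to drug-related events and commits to no all-cause table. Protocol 7.3.2 and 9.7 call for the all-cause incidence, and SAP 4.8 does not declare the change. It is a conflict between a stated restriction and the protocol's measure, not merely missing detail.

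The size of the difference cannot be determined from the documents. It is zero if every patient who discontinues because of an adverse event has such an event judged related. On the prior study's 20.3%, a related-only table would show about 5% to 20% for shares of 25% to 100%. That range of shares is an assumption without a source in the documents, and the illustration also takes the 13 withdrawals to be all-cause. The change is worth making because the data are already planned for listing and the remedy is cheap.

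**What to change.** In SAP 4.6.2:

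1. Add the patient incidence of TEAEs leading to discontinuation of nanatinostat, of valganciclovir, and of either drug, regardless of relationship, by system organ class and preferred term. This matches the layout of the interruption and reduction tables.
2. Name all-cause discontinuation as a criterion in the overall TEAE summary.
3. State that these outputs serve the tolerability measure in Protocol 7.3.2.
4. Keep the three related-only tables as supportive.

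If the sponsor prefers related-only tables, SAP 4.8 should declare and justify the departure from the protocol.

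The cost is three tables and one row. Adverse events leading to permanent discontinuation are already to be listed, so no new data should be needed. The reported rate may be less favourable than the related-only one.
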